The sample size calculation for this hypothesis is based on the one-sample t-test for equivalence. The desired outcome is to reject the null hypothesis at the 0.05 significance level. For this equivalence test of bias, two comparisons will be performed: FloTrac vs Swan-Ganz and ClearSight vs Swan-Ganz. In order to preserve the overall type 1 error rate at 0.05, the Bonferroni Correction will be used to adjust for multiple comparisons.

THIS DOCUMENT CONTAINS CONFIDENTIAL AND PROPRIETARY INFORMATION OF EDWARDS LIFESCIENCES, LLC. IT MAY NOT BE REPRODUCED OR DISCLOSED WITHOUT PRIOR WRITTEN PERMISSION FROM EDWARDS LIFESCIENCES, LLC.

POGO Study
Study #2019-08

Assuming a true mean bias of 0.0 and a SD of 1.0 l/min in the cardiac output, the sample size required for δ =0.5, alpha=0.05, and power=90% to reject the null hypothesis is 45, ignoring the ICC. After considering ICC for eight repeated measures (m=8), a sample size of 54 Subjects in needed. After considering a 34.5% rejection rate for hemodynamic instability, 10% lost to follow-up rate and 6 Roll-in Subjects for the learning curve, a total of 102 (96 evaluable Pivotal Subjects and 6 Roll-in Subjects) will be enrolled.

Adjusting for multiple comparisons, considering there will be two target devices and a reference device pairs, simultaneously, 108 total Subjects will be enrolled in this study.

Sample size consideration for percent error

The Critchley and Critchley method of percent error (PE) calculation will be compared to 30%. The Precision will be considered as acceptable if PE is less than 30 %.

The hypothesis for PE is a one-sided test:

H0: PE > 30%H1: PE $\leq 30\%$

The sample size calculation for this hypothesis was based on the one-sided T-test. The desired outcome is to reject the null hypothesis at the 0.05 significance level. Assuming a true mean of 30% and a conservative SD assumption of 70%, the sample size required for power=90% to reject the null hypothesis is 49.

Because the study is designed with sub samples (repeated measurements) or sub sample sections (m= 8), ICC is a factor needing to be considered in the sample size estimation. When eight repeated measures (m=8) are performed, the SD=69.38%. The corresponding sample size necessary is 49.

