The sample size calculation for this hypothesis is based on the one-sample t-test for equivalence. The desired outcome is to reject the null hypothesis at the 0.025 significance level. For this equivalence test of bias, two comparisons will be performed: FloTrac vs Swan-Ganz and ClearSight vs Swan-Ganz. In order to preserve the overall type 1 error rate at 0.05, the Bonferroni Correction will be used to adjust for multiple comparisons. Assuming a true mean bias of 0.0 and a SD of 1.0 l/min in the cardiac output, the sample size required for δ =0.5, alpha=0.025, and power=90% to reject the null hypothesis is 45, ignoring the ICC. After considering ICC for eight repeated measures (m=8), adjusting for multiple comparisons, considering comparisons of between two target devices and a reference device pairs, simultaneously, a sample size of 60 Subjects is needed. After considering a 34.5% rejection rate for hemodynamic instability, 10% lost to follow-up rate, and 6 roll-in Subjects for the learning curve, up to 108 (102) evaluable Pivotal Subjects and 6 Roll-in Subjects) will be enrolled into the study.

By simulating the study results with a mixed effect model, using repeated measurement data collected from a similar study, although the sample size estimate from this approach is conservative, it is reasonable and rational.

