8.1.2 Primary endpoint analysis with Bias calculated by CO

The primary endpoint of the bias between the matched pairs of CO measurements as determined by the Bland-Altman method will be tested as below using the one sample t-test.

The hypothesis for bias is:

H0: bias <-0.5 or bias >0.5

H1: -0.5≤ bias ≤0.5

See section 3.1 for details.

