8.1.3 Limits of Agreement

Limits of agreement will be computed using Bland-Altman methods. Components of the one-way analysis of variance will be used to estimate variance of multiple between-device differences for the same subject. These components of variance measures include the mean square for subjects (SS), and residual mean square (RMS). The differences between the average difference across subjects will be estimated from the difference between SS and RMS. This difference will be divided by $M=((\sum m_i)^2 - \sum m_i^2)/(n-1)^*(\sum m_i)$, where n=1 total number of subjects, and m_i is the number of pairwise difference measurements for the *ith* subject. The estimated component of variance, which represents the heterogeneity, is estimated as (SS – RMS)/M. The total variance (TV) for single differences on different subjects is estimated by the sum of these two components: TV = (SS – RMS)/M + RMS. The resulting lower and upper limits of agreement will be estimated with 97.5% confidence mean(diff) \pm 1.984*TV for a two-sided test.

Revision Date: December 2, 2020

Rev

For Use Only by Affiliates of Edwards Lifesciences

Page 22

Title

Statistical Analysis Plan for A Prospective, Single-Arm, Nonrandomized, Observational Study of Cardiac Output Monitoring in Pediatric Patients

В

We want agreement to be the same or at least similar over the range of CO and CI measurements. Plots of the difference bias between device pairings (ClearSight vs Swan-Ganz, and FloTrac vs Swan-Ganz), for CO and CI measurements, on average of the two device measurements will be performed, with reference lines including zero, mean difference, and lower and upper limits of agreement. Two-sided 97.5% LOA will be calculated for bias between device pairings⁹. The statisticians will determine whether the standard deviation of the mean difference is constant or non-constant for each measure. The mean difference and standard deviation about the mean difference will be estimated for all measurements. The difference measures will be tested for heterogeneity using components of variance methods. The variance for single differences between device pairs of measurements, on different subject, will be plotted. Also, mean difference will be plotted on the order in which observations are recorded for each subject.

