Visual check of the bias spread pattern and deviation using scatter plots of bias and/or percent error versus Fick principle reference mean CO, and scatter plot of bias and the percent error versus target device mean CO, with reference lines zero and limits of agreement ($\delta \Theta \delta \delta$) to the plot will be performed.

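### SAP 8.1.3 wants agreement to be similar over the CO range but leaves CO-dependent bias to plots, one of which slopes upward by construction

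*Combined protocol and SAP*

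**What the plan says.** **Primary decision.** Under SAP 8.1.2 the bias between matched CO pairs "will be tested as below using the one sample t-test", with "H1: -0.5≤ bias ≤0.5" as the alternative. The decision rests on one mean difference per device pair.

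**Agreement over the range.** SAP 8.1.3 states the aim: "We want agreement to be the same or at least similar over the range of CO and CI measurements". What follows is:
- a plot of the difference against the average of the two devices, for CO and CI and each device pair, with lines at zero, the mean difference and the limits of agreement;
- a decision by the statisticians on whether the SD is constant, with no method or consequence given;
- a heterogeneity test by components of variance (subject against residual);
- a visual check against Fick CO, and a "scatter plot of bias and the percent error versus target device mean CO".

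**Elsewhere.** The subgroups in SAP 8.4 and in the protocol's Additional Evaluations are age, gender, race and site. The mixed model in SAP 8.4.2 has site, surgery team and subject as factors. CO level appears in neither, and no slope of bias on CO is estimated.

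**The concern.** A device that over-reads at low CO and under-reads at high CO can have a mean difference near zero. The primary test cannot see this, so the stated aim depends on the supporting displays, and these carry no estimate or interval. One display is also misleading. When T - R is plotted against T, the error of T enters both axes with the same sign, so the points slope upward even when bias does not depend on CO. That can suggest a fault in a sound device, or offset a real negative slope. The SAP does not say which plot prevails if they disagree.

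At stake is how far the comparability result can be read across the CO range of patients aged 12 to 18, the group to which the indications are to be extended.

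**Working it through.** **Inputs from the documents.** Margin ±0.5 L/min (SAP 8.1.2). "Assuming a true mean bias of 0.0 and a SD of 1.0 l/min in the cardiac output" (SAP 2.3.1). SAP 2.3.1 sets 0.025 per comparison ("The desired outcome is to reject the null hypothesis at the 0.025 significance level"); Protocol Section 6 writes 0.05 and adds Bonferroni ("The desired outcome is to reject the null hypothesis at the 0.05 significance level"). The SAP requires 60 subjects, and 60 / (0.655 × 0.90) = 101.8 gives the 102 pivotal subjects.

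**Assumed, because the documents give no figure.** SD of true CO 1.2 L/min (range 0.8 to 2.0). Difference variance split 50:50 between target and reference (range 25:75 to 75:25). Bias linear in CO and zero at the mean.

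**Step 1: the plan's own figure.** Exact power of the one-sample equivalence t-test with SD 1.0, margin 0.5 and true bias 0 is 0.9025 at n = 45 and alpha 0.05. This reproduces the protocol's "power=90% to reject the null hypothesis is 45, ignoring the ICC". At alpha 0.025, power at 45 is 0.813 and 54 subjects are needed, so the SAP's 45 does not match its own alpha. That is a separate matter. Below, alpha is 0.025; power at n = 60 is then 0.936.

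**Step 2: slope built into the target-device plot.** Let C be true CO, T = C + e_T and R = C + e_R, with no CO-dependent bias.
- Slope of T - R on T = var(e_T) / [var(C) + var(e_T)] = 0.5 / (1.44 + 0.5) = **+0.26**. Over the assumed ranges it is 0.06 to 0.54, always positive.
- If a reader tested that slope at two-sided 0.05, it would be significant in about 81% of trials at n = 60 and 96% at n = 102.
- Slope on the two-device average = [var(e_T) - var(e_R)] / {2 × [var(C) + (var(e_T) + var(e_R))/4]}. It is 0 when the error variances are equal.

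**Step 3: cancellation in the mean.** Take a true slope of -0.4. Bias at the 10th and 90th CO percentiles is ±0.4 × 1.2816 × 1.2 = ±0.615, about **±0.62 L/min**, outside the margin. Two cases:
- slope added to SD 1.0: total SD = √(1 + 0.48²) = 1.109;
- total SD held at 1.0: error variance falls to 1 - 0.2304 = 0.7696.

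| True slope -0.4, CO SD 1.2, 50:50 | Slope added | Total SD held |
|---|---|---|
| Primary test passes, n = 60 | 86% | 94% |
| Primary test passes, n = 102 | 99% | 99.8% |
| Slope on two-device average detected, n = 60 | 87% | 94% to 95% |
| Slope shown on target-device plot | +0.15 | +0.04 |

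Last row: (-0.4 × 0.6 × 1.44 + 0.5) / (0.36 × 1.44 + 0.5) = 0.154 / 1.018 = +0.15, and (-0.346 + 0.385) / (0.518 + 0.385) = +0.04. The real negative slope is hidden.

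**Step 4: sensitivity to the assumed CO spread (slope added, n = 60).**
- CO SD 0.8: bias at those percentiles is 0.41, inside the margin; slope power is 46%.
- CO SD 2.0: bias is 1.03; the primary test passes in 69% of trials. The target-device plot then shows (-0.96 + 0.5) / (1.44 + 0.5) = -0.24, the right sign but too shallow.

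**Step 5: does the heterogeneity test fill the gap?** It compares subjects, not CO levels. At the SAP's planning values (ICC 0.98, m = 8) its expected F is about 1 + 8 × 0.98 / 0.02 = 393, so it would be significant whether or not bias depends on CO.

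**Step 6: limit of the proposed regression.** With no CO-dependent bias, CO SD 1.2 and the target device carrying 75% of the error variance, the slope on the average is +0.15. It is falsely significant in about 32% of trials at n = 60 and 49% at n = 102.

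**The case against.** The plan does address the CO range. Difference against the two-device average is the standard Bland-Altman display and the main plot here. The Fick plot avoids shared error if Fick errors are independent of both devices. A marked slope would be visible in both. The target-device plot is one supplementary display and feeds no decision. This all stands, and it is why the point is an improvement and not an error in the primary analysis.

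The primary endpoint is defined as mean bias, so opposite biases cancelling is a property of the endpoint chosen. A reader might infer that the primary test is invalid; the documents do not support that, since the test answers the question it poses.

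The secondary percent error uses absolute differences, which cannot cancel. That is partial protection: with an assumed mean CO of 5 L/min, slope -0.4 added and n = 60, it still passes in 80% of simulated trials (98% with no slope), and it does not gate the primary result.

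A reader might also want comparability claimed only where predicted bias lies within 0.5 L/min. Step 6 shows why an automatic rule would be unsound: the slope on the average is itself biased when error variances differ. The documents give no ground for assuming them equal, since the reference averages three bolus injections and the targets average 30-second continuous readings.

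**Conclusion.** The point holds as a cheap improvement. SAP 8.1.3 states an aim of similar agreement over the CO range, and nothing in the plan estimates how bias changes with CO. Two of its plots suit the purpose. The third has a positive slope by construction, about +0.26 under the central assumptions and 0.06 to 0.54 over the ranges. A slope of -0.4, putting bias about 0.62 L/min from zero at the 10th and 90th percentiles, would pass the primary test in 86% to 94% of trials at n = 60, against 94% with no slope.

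The sizes rest on an assumed CO spread and error split. The positive sign of the artefact under no CO-dependent bias does not. Whether a given slope takes bias outside the margin does depend on the spread: at CO SD 0.8, a slope of -0.4 does not do so at those percentiles. Nothing here shows that either device has CO-dependent bias.

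**What to change.** In SAP 8.1.3, as a prespecified supportive analysis beside the primary result:
- For each device pair, regress each subject's mean difference on that subject's two-device average. Report the slope with its confidence interval, and the predicted bias with its interval at the 10th and 90th percentiles of CO.
- State that this slope is biased if the two devices' error variances differ, by -0.28 to +0.28 over the ranges assumed here. Add a sensitivity analysis, such as the same regression on Fick CO where available, or an errors-in-variables fit using the repeat measurements. Repeats inform only within-subject error, which is the small part at the planning ICC of 0.98, so that fit should also be run over a range of error-variance ratios.
- Give regression-based limits of agreement as a supplement when a slope is evident.
- Drop the plot against target-device CO, or replace its axis with the two-device average.

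Do not add a rule that automatically narrows the comparability statement.

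**Cost.** A little more analysis on data already collected, with no new subjects or visits. A reported slope may qualify how the comparability result is read.

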8.2 Secondary Endpoint

8.2.1 Percent Error calculated by CO as the secondary endpoint

The secondary endpoint of the percent error between the matched pairs of CO measurements as determined by the Critchley and Critchley method will be tested as below using the one sample t-test. The hypothesis for PE is:

H0: PE > 30% H1: PE ≤ 30%

8.3 Sensitivity Analysis

8.3.1 Sensitivity analysis on study subject

To determine the effectiveness of study subject on the analytical results, following sensitivity analysis will be conducted by artificially removing one or a few study subjects. The expected result is that no study subject or group of study subjects are influence subjects on the analytical result.

8.3.2 Sensitivity analysis on reference device

To determine the effectiveness of reference device on the test device in the analytical results, different reference devices will be applied in sensitivity analysis. The expected result is that the reference device performance is stable and consistency, which is not the influence factor for the analytical result.

8.4 Exploratory Analyses

	Revision Date: De	ecember 2, 2020	Rev	В	For Use Only by Affiliates of Edwards Lifesciences	Page 23
Edwards	Title	Statistical Analysis Pl Nonrandomized, Obso Monitoring in Pediatri	ervatio	onal St		

The following exploratory analyses will be preformed

- Comparison analysis of CI calculated for Bias as determined by Bland Altman method with confidence intervals.
- Comparison analysis of CI as determined by the Critchley and Critchley method of percent error calculation with confidence intervals
- Subgroup analysis of primary and secondary endpoint by age stratification
- Subgroup analysis of primary and secondary endpoint by gender
- Subgroup analysis of primary and secondary endpoint by race
- Subgroup analysis of primary and secondary endpoint by site
- Comparison of cardiac output from FloTrac, ClearSight and Swan-Ganz technologies to the Fick principle

8.4.1 Validation of Accuracy and Consistency

Considering the variation of CO measurement from both device systems among patients, applying patient and patient age group as potential classification factors, the conclusion from 8.1.2 will be validated with bootstrap method through the 97.5% coverage intervals, which should be within the range from - δ to δ . These analyses will be presented within clinical study report.

8.4.2 Variance component analysis

With mixed effect model, the derived variable bias as the response, study site, surgery team, and subject as the random variable, estimate the variance component of each factor to trace the main source of variability, which will benefit to future variation control. This analysis will be present in the clinical study report.

8.5 Interim analysis

No interim analysis is planned for this study.

8.6 Analysis of other hemodynamic parameters

Revision Date: December 2, 2020

Rev

For Use Only by Affiliates of Edwards Lifesciences

Page 24

Title

Statistical Analysis Plan for A Prospective, Single-Arm, Nonrandomized, Observational Study of Cardiac Output Monitoring in Pediatric Patients

В

Below is a table of other hemodynamic parameters measures that will be collected in this study.

Table 1. Measures by Device and Endpoint							
rable 1. measures by Bernet		ароппе	Device				
Parameters	Swan Ganz	FloTrac	ClearSight	ForeSight	Endpoints		
Cardiac Output (CO)	Х	Х	Х		Primary (Bland Altman), Secondary (Percent Error)		
Cardiac Index (CI)	Х	Х	Х		None (exploratory analyses - descriptive stats)		
Central Venous Pressure (CVP)		Х			None (exploratory analyses - descriptive stats)		
Diastolic Blood Pressure (DIA(ART)/DIA(PAP))		Х			None (exploratory analyses - descriptive stats)		
Dynamic Arterial Elastance (Ea(dyn))		Х	Х		None (exploratory analyses - descriptive stats)		
Intermittent cardiac index (iCl)	Х				None (exploratory analyses - descriptive stats)		
Intermittent cardiac output (iCO)	Х				None (exploratory analyses - descriptive stats)		
Intermittent systemic vascular resistance (iSVR)	Х				None (exploratory analyses - descriptive stats)		
Intermittent systemic vascular resistance index (iSVRI)	X				None (exploratory analyses - descriptive stats)		
Mean Arterial Pressure (MAP)		Х	Х		None (exploratory analyses - descriptive stats)		
Mean pulmonary artery blood pressure (MPAP)		Х			None (exploratory analyses - descriptive stats)		
Noninvasive Arterial Diastolic Pressure (DIA(NI))			Х		None (exploratory analyses - descriptive stats)		
"Noninvasive arterial systolic blood pressure (SYS(NI))"			X		None (exploratory analyses - descriptive stats)		
Pulmonary artery diastolic blood pressure (DIA(PAP))		Х			None (exploratory analyses - descriptive stats)		
Pulmonary artery systolic blood (SYS(PAP))		Х			None (exploratory analyses - descriptive stats)		
Pulse Pressure Variation (PPV)		Х	Х		None (exploratory analyses - descriptive stats)		
Pulse Rate (PR)	X	Х	Х		None (exploratory analyses - descriptive stats)		
Stroke volume (SV)	Х	Х	Х		None (exploratory analyses - descriptive stats)		
Stroke volume index (SVI)	X	X	Χ		None (exploratory analyses -		

	Revision Date: De	ecember 2, 2020	Rev	В	For Use Only by Affiliates of Edwards Lifesciences	Page 25	
8	Title	l -	lan for A Prospective, Single-Arm, ervational Study of Cardiac Output				

Monitoring in Pediatric Patients

Table 1. Measures by Device and Endpoint						
				descriptive stats)		
Stroke Volume Variation	Х	Χ		None (exploratory analyses -		
(SVV)				descriptive stats)		
Systemic arterial diastolic	X			None (exploratory analyses -		
blood pressure (DIA (ART))				descriptive stats)		
Systemic arterial systolic	X			None (exploratory analyses -		
blood pressure (SYS(ART))				descriptive stats)		
Systemic vascular	X	Χ		None (exploratory analyses -		
resistance (SVR)				descriptive stats)		
Systemic vascular	X	Χ		None (exploratory analyses -		
resistance index (SVRI)				descriptive stats)		
Systolic Pressure	X			None (exploratory analyses -		
(SYS(ART)/SYS(PAP))				descriptive stats)		
Systolic Slope (dP/dt)	X	Χ		None (exploratory analyses -		
				descriptive stats)		
StO2 - 1 (cerebral)			Х	None (exploratory analyses -		
				descriptive stats)		
StO2 - 2 (cerebral)			Х	None (exploratory analyses -		
				descriptive stats)		

9 ANALYSIS OF SAFETY

9.1 Adverse Events

[figure not shown]
The adverse events data will be summarized with frequency counts and percentages. The frequency distribution and percentage of adverse event related to a specific medical device will be presented. The primary safety endpoint will include summary of intraoperative and post-operative adverse events, discharge through 30 days followup, related or unrelated to the devices under study.

9.2 Deaths and Other Serious Adverse Events

Death or other serious adverse events that occur during this study will be summarized with frequencies and percentages.

10 CHANGES FROM PROTOCOL SPECIFIED ANALYSES

There are no changes to the protocol specified analyses at this time.

Edwards	Title		lan for A Prospective, Single-Arm, ervational Study of Cardiac Output ic Patients				

[figure not shown]
12 APPENDIX

13 LITERATURE SEARCH/REVIEW

For the original FloTrac submission in 2004 and the publication (Nusmeier, van Der Hoeven, and Lemson, 2010), an abstract search was performed to compile relevant clinical data on the accuracy and acceptance criteria of various injectate and continuous cardiac output measurements (iCO, and CCO). PubMed was searched using the keywords "continuous" OR "Fick' OR pulse contour" OR "TD") AND "cardiac output" AND "precision", to identify published literature that reported performance comparisons of cardiac output measurements. A total of 97 abstracts of published articles were found as a result of the search.

Review of the abstracts showed that 42 of them were irrelevant. Of the 42 that were not taken into consideration, 17 reported on pre-clinical studies, 21 had insufficient statistics and 4 did not provide performance comparison of cardiac output. Hence, 55 abstracts were deemed relevant to this analysis. Ten out of 55 abstracts reported accuracy in terms of cardiac index. The remaining 45 abstracts contained 75 pairs of Bland-Altman comparisons. Fourteen of the 75 Bland-Altman comparison pairs were reported as marginal or unacceptable, the remaining 61 pairs from 38 abstracts were reported as clinically acceptable [32-69].

Figure 1 indicates a histogram of the bias reported in the 61 comparisons. The range of bias reported as clinically acceptable was [-0.79 ...0.63]. However, from the histogram, it can be seen that only three of the reported values were outside +/- 0.6 l/min. Thus, the literature advocated outer limits of +/- 0.6 l/min for the bias of a Bland-Altman comparison of cardiac output values.

Since then, several CO validation studies against pulmonary and transpulmonary thermodilution with the noninvasive technology have been performed. The analysis of 10 of these studies [70-79] showed a bias range of 0.0 to 0.6 L/min, with an average of 0.24 \pm 0.19 L/min. Based on these data and after discussion with the Data Management and Bio-center of the National Center for Cardiovascular

	Revision Date: December 2, 2020			В	For Use Only by Affiliates of Edwards Lifesciences	Page 28	
Edwards	Title		lan for A Prospective, Single-Arm, ervational Study of Cardiac Output ic Patients				

Diseases ([name] LI), the performance criterion was set at 0.5 L/min, i.e. bias is determined to be -0.5< bias < 0.5 l/min. This value is smaller in magnitude to the 0.8 l/min floor that the US FDA had previously considered for CO comparisons.

